**8 LIST OF FIGURES**

FIGURE 1 MEDIAN PERCENT REDUCTION FROM BASELINE IN SEIZURE  
FREQUENCY OVER TIME BY DURATION OF TREATMENT EXPOSURE

## 9 LIST OF PATIENT DATA LISTINGS

- LISTING 1 PATIENT WITHDRAWAL/STUDY COMPLETION
- LISTING 2 INCLUSION/EXCLUSION CRITERIA/ELIGIBILITY
- LISTING 3 DEMOGRAPHICS AND BASELINE CHARACTERISTICS
- LISTING 4 STUDY MEDICATION COMPLIANCE
- LISTING 5 CONCOMITANT MEDICATIONS EXCLUDING BACKGROUND  
ANTI-EPILEPTIC DRUGS (AEDs)
- LISTING 6 CONCOMITANT TREATMENTS OTHER THAN MEDICATION
- LISTING 7 PARTIAL SEIZURE FREQUENCY
- LISTING 8 GENERALIZED OR UNCLASSIFIED SEIZURE FREQUENCY
- LISTING 9 EXTENT OF EXPOSURE TO STUDY MEDICATION
- LISTING 10 ADVERSE EVENTS CODING DICTIONARY MAPPING
- LISTING 11 ADVERSE EVENTS
- LISTING 12 TREATMENT-EMERGENT ADVERSE EVENTS
- LISTING 13 TREATMENT-EMERGENT ADVERSE EVENTS AT LEAST  
POSSIBLY RELATED TO STUDY MEDICATION
- LISTING 14 TREATMENT-EMERGENT ADVERSE EVENTS THAT CAUSED  
WITHDRAWAL FROM STUDY
- LISTING 15 TREATMENT-EMERGENT ADVERSE EVENTS THAT LEAD TO  
DOSE MODIFICATION/INTERRUPTION
- LISTING 16 DEATHS
- LISTING 17 SERIOUS TREATMENT-EMERGENT ADVERSE EVENTS
- LISTING 18 LABORATORY REFERENCE RANGES
- LISTING 19 HEMATOLOGY LABORATORY TEST RESULTS
- LISTING 20 BLOOD SERUM CHEMISTRY LABORATORY TEST RESULTS
- LISTING 21 URINALYSIS LABORATORY TEST RESULTS
- LISTING 22 ECG DIAGNOSIS/COMMENTS INFORMATION
- LISTING 23 ECG RESULTS
- LISTING 24 ECGS NOT PERFORMED AND THEIR REASON FOR NOT  
PERFORMING
- LISTING 25 ECG RESULTS FOR PATIENTS WITH QTC INTERVAL  
>500MSEC OR CHANGE FROM BASELINE IN QTC INTERVAL >60MSEC
- LISTING 26 VITAL SIGNS
- LISTING 27 ABNORMAL PHYSICAL EXAMINATION RESULTS
- LISTING 28 ABNORMAL NEUROLOGICAL EXAMINATION RESULTS
- LISTING 29 AUA SYMPTOM INDEX
- LISTING 30 PVR BLADDER ULTRASOUND RESULTS

LISTING 31 QUALITY OF LIFE IN EPILEPSY SCORES (QOLIE-31-P)

## 10 TABLE SHELLS

31

**CONFIDENTIAL**

RM2009/00475/00  
VRX-RET-E22-304

Valeant Pharmaceuticals North America  
 Protocol Number: VRX-RET-E22-304

PAGE X OF X

TABLE 1 NUMBER (%) OF PATIENTS WHO DISCONTINUED TREATMENT DURING THERAPY PHASE BY PRIMARY REASON  
 SAFETY POPULATION

	RETIGABINE (N=XXX)
DISCONTINUED ANY REASON	xx (xx.x%)
ADVERSE EVENT	xx (xx.x%)
UNSATISFACTORY RESPONSE - EFFICACY	xx (xx.x%)
PREGNANT	xx (xx.x%)
UNWILLING OR UNABLE TO CONTINUE THE STUDY	xx (xx.x%)
NON-COMPLIANT WITH STUDY PROCEDURES	xx (xx.x%)
REQUIRES MEDICATION NOT ALLOWED IN THE PROTOCOL	xx (xx.x%)
CLINICALLY SIGNIFICANT CHANGE IN MEDICAL CONDITION	xx (xx.x%)
PERSISTENT ALT OR AST ABOVE 3xULN	xx (xx.x%)
ALT OR AST ABOVE 5xULN AT ANY TIME	xx (xx.x%)
CONFIRMED QTC PROLONGATION	xx (xx.x%)
INVESTIGATOR DECISION	xx (xx.x%)
SPONSOR REQUEST	xx (xx.x%)
FAILURE TO RETURN	xx (xx.x%)
PATIENT REQUEST UNRELATED TO STUDY	xx (xx.x%)
OTHER EVENT	xx (xx.x%)

32

CONFIDENTIAL

RM2009/00475/00  
 VRX-RET-E22-304

Program Path/sas program name

Run Date:

TABLE 2 TIME UNTIL TREATMENT DISCONTINUATION (DAYS) DESCRIPTIVE STATISTICS  
SAFETY POPULATION

STATISTICS	RETIGABINE (N=XXX)
N	xxx
MEAN	xxx.x
STD	xxx.xx
MEDIAN	xxx.x
MINIMUM	xxx
MAXIMUM	xxx

Valeant Pharmaceuticals North America  
 Protocol Number: VRX-RET-E22-304

PAGE X OF X

TABLE 3 DEMOGRAPHIC AND BASELINE CHARACTERISTICS  
 SAFETY POPULATION

STATISTICS	RETIGABINE (N=XXX)
AGE - YEAR	
N	xxx
MEAN	xxx.x
STD	xxx.xx
MEDIAN	xxx.x
MINIMUM	xxx
MAXIMUM	xxx
SEX - N (%)	
MALE	xxx (xx.x%)
FEMALE	xxx (xx.x%)
RACE - N (%)	
CAUCASIAN	xxx (xx.x%)
AFRICAN-AMERICAN (BLACK)	xxx (xx.x%)
HISPANIC	xxx (xx.x%)
ASIAN	xxx (xx.x%)
OTHER	xxx (xx.x%)
HEIGHT - CM	
N	xxx
MEAN	xxx.x
STD	xxx.xx
MEDIAN	xxx.x
MINIMUM	xxx
MAXIMUM	xxx
WEIGHT - KG	
N	xxx
MEAN	xxx.x
STD	xxx.xx
MEDIAN	xxx.x
MINIMUM	xxx
MAXIMUM	xxx

Program Path/sas program name

Run Date:

TABLE 3 DEMOGRAPHIC AND BASELINE CHARACTERISTICS  
SAFETY POPULATION

STATISTICS	RETIGABINE (N=XXX)
BMI - (KG/M^2)	
N	xxx
MEAN	xxx.x
STD	xxx.xx
MEDIAN	xxx.x
MINIMUM	xxx
MAXIMUM	xxx

35

CONFIDENTIAL

RM2009/00475/00  
VRX-RET-E22-304

Valeant Pharmaceuticals North America  
 Protocol Number: VRX-RET-E22-304

PAGE X OF X

TABLE 4 EPILEPSY HISTORY  
 SAFETY POPULATION

TYPE OF EPILEPSY STATISTICS	RETIGABINE (N=XXX)
PARTIAL (PRIMARY DIAGNOSIS)	
DURATION - YEARS	
N	xxx
MEAN	xxx.x
STD	xxx.xx
MEDIAN	xxx.x
MINIMUM	xxx
MAXIMUM	xxx
GENERALISED	
DURATION - YEARS	
N	xxx
MEAN	xxx.x
STD	xxx.xx
MEDIAN	xxx.x
MINIMUM	xxx
MAXIMUM	xxx

36

CONFIDENTIAL

RM2009/00475/00  
 VRX-RET-E22-304

Program Path/sas program name

Run Date:

Valeant Pharmaceuticals North America  
Protocol Number: VRX-RET-E22-304

PAGE X OF X

FOOTNOTES:

A PATIENT CAN HAVE EPILEPSY HISTORY RECORDED FOR EACH TYPE OF EPILEPSY.

Valeant Pharmaceuticals North America  
 Protocol Number: VRX-RET-E22-304

PAGE X OF X

TABLE 5 CLINICAL GLOBAL IMPRESSION (CGI) - SEVERITY AT BASELINE  
 SAFETY POPULATION

STATISTICS	RETIGABINE (N=XXX)
CGI-SEVERITY	
N	xxx
MEAN	xxx.x
STD	xxx.xx
MEDIAN	xxx.x
MINIMUM	xxx
MAXIMUM	xxx
CGI-SEVERITY	
AMONG THE MOST EXTREMELY SEVERE	xxx (xx.x%)
VERY SEVERE	xxx (xx.x%)
MARKED SEVERITY	xxx (xx.x%)
MODERATE SEVERITY	xxx (xx.x%)
MILD SEVERITY	xxx (xx.x%)
VERY MILD SEVERITY	xxx (xx.x%)
NO SEIZURES	xxx (xx.x%)
NOT ASSESSED	xxx (xx.x%)

38

CONFIDENTIAL

RM2009/00475/00  
 VRX-RET-E22-304

Program Path/sas program name

Run Date:

Valeant Pharmaceuticals North America  
 Protocol Number: VRX-RET-E22-304

PAGE X OF X

TABLE 6 NUMBER OF BACKGROUND AEDs AT BASELINE N (%)  
 SAFETY POPULATION

CATEGORY	RETIGABINE (N=XXX)
NUMBER OF AEDs	
1	xxx (xx.x%)
2	xxx (xx.x%)
3	xxx (xx.x%)
VAGAL NERVE STIMULATOR USED?	
YES	xxx (xx.x%)
NO	xxx (xx.x%)

39

CONFIDENTIAL

RM2009/00475/00  
 VRX-RET-E22-304

Program Path/sas program name

Run Date:

Valeant Pharmaceuticals North America  
 Protocol Number: VRX-RET-E22-304

PAGE X OF X

TABLE 7 PRESENCE OF PARTIAL SEIZURE BY SUBTYPE DURING BASELINE PERIOD  
 SAFETY POPULATION

CATEGORY	RETIGABINE (N=XXX)
BASELINE PERIOD	
N	xxx
SIMPLE PARTIAL SEIZURES WITH MOTOR SIGNS	xxx (xx.x%)
SIMPLE PARTIAL SEIZURES WITHOUT MOTOR SIGNS	xxx (xx.x%)
SIMPLE PARTIAL SEIZURES WITH AND WITHOUT MOTOR SIGNS	xxx (xx.x%)
COMPLEX PARTIAL SEIZURES	xxx (xx.x%)
PARTIAL SEIZURES EVOLVING TO SECONDARY GENERALISED	xxx (xx.x%)

40

CONFIDENTIAL

RM2009/00475/00  
 VRX-RET-E22-304

Program Path/sas program name

Run Date:

Valeant Pharmaceuticals North America  
Protocol Number: VRX-RET-E22-304

PAGE X OF X

FOOTNOTES: A PATIENT CAN APPEAR IN MULTIPLE CATEGORIES.

41

CONFIDENTIAL

RM2009/00475/00  
VRX-RET-E22-304

---

Program Path/sas program name

Run Date:

---

Filename: 87272\_304\_SAP\_v2\_final

page 40 of 148

Valeant Pharmaceuticals North America  
 Protocol Number: VRX-RET-E22-304

PAGE X OF X

TABLE 8 PERCENTAGE CHANGE IN MONTHLY TOTAL PARTIAL SEIZURE FREQUENCY  
 SAFETY POPULATION

STATISTICS	RETIGABINE (N=XXX)		
	OBSERVED	CHANGE FROM BASELINE	PERCENTAGE CHANGE FROM BASELINE
BASELINE [1]			
N	xxx		
MEAN	xxx.x		
STD	xxx.xx		
MEDIAN	xxx.x		
MINIMUM	xxx		
MAXIMUM	xxx		
OPEN-LABEL PHASE			
N	xxx	xxx	xxx
MEAN	xxx.x	xxx.x	xxx.x
STD	xxx.xx	xxx.xx	xxx.xx
MEDIAN	xxx.x	xxx.x	xxx.x
MINIMUM	xxx	xxx	xxx
MAXIMUM	xxx	xxx	xxx

42

CONFIDENTIAL

RM2009/00475/00  
 VRX-RET-E22-304

Valeant Pharmaceuticals North America  
Protocol Number: VRX-RET-E22-304

PAGE X OF X

FOOTNOTE:

[1] BASELINE PHASE IN STUDY VRX-RET-E22-302

43

CONFIDENTIAL

RM2009/00475/00  
VRX-RET-E22-304

---

Program Path/sas program name

Run Date:

---

Filename: 87272\_304\_SAP\_v2\_final

page 42 of 148

Valeant Pharmaceuticals North America  
 Protocol Number: VRX-RET-E22-304

PAGE X OF X

TABLE 9.1 PERCENTAGE CHANGE IN MONTHLY TOTAL PARTIAL SEIZURE FREQUENCY FOR PATIENTS TREATED WITH RETIGABINE FOR AT LEAST 1 MONTH DURING THE OPEN-LABEL EXTENSION SAFETY POPULATION

STATISTICS	RETIGABINE (N=XXX)		
	OBSERVED	CHANGE FROM BASELINE	PERCENTAGE CHANGE FROM BASELINE
BASELINE [1]			
N	xxx		
MEAN	xxx.x		
STD	xxx.xx		
MEDIAN	xxx.x		
MINIMUM	xxx		
MAXIMUM	xxx		
MONTH 1			
N	xxx	xxx	xxx
MEAN	xxx.x	xxx.x	xxx.x
STD	xxx.xx	xxx.xx	xxx.xx
MEDIAN	xxx.x	xxx.x	xxx.x
MINIMUM	xxx	xxx	xxx
MAXIMUM	xxx	xxx	xxx

44

CONFIDENTIAL

RM2009/00475/00  
 VRX-RET-E22-304

Program Path/sas program name

Run Date:

Valeant Pharmaceuticals North America  
Protocol Number: VRX-RET-E22-304

PAGE X OF X

FOOTNOTE: [1] BASELINE PHASE IN STUDY VRX-RET-E22-302

45

CONFIDENTIAL

RM2009/00475/00  
VRX-RET-E22-304

---

Program Path/sas program name

Run Date:

---

Filename: 87272\_304\_SAP\_v2\_final

page 44 of 148

Valeant Pharmaceuticals North America  
 Protocol Number: VRX-RET-E22-304

PAGE X OF X

TABLE 9.2 PERCENTAGE CHANGE IN MONTHLY TOTAL PARTIAL SEIZURE FREQUENCY FOR PATIENTS TREATED WITH RETIGABINE FOR AT LEAST 3 MONTHS DURING THE OPEN-LABEL EXTENSION SAFETY POPULATION

STATISTICS	RETIGABINE (N=XXX)		
	OBSERVED	CHANGE FROM BASELINE	PERCENTAGE CHANGE FROM BASELINE
BASELINE [1]			
N	xxx		
MEAN	xxx.x		
STD	xxx.xx		
MEDIAN	xxx.x		
MINIMUM	xxx		
MAXIMUM	xxx		
MONTH 1			
N	xxx	xxx	xxx
MEAN	xxx.x	xxx.x	xxx.x
STD	xxx.xx	xxx.xx	xxx.xx
MEDIAN	xxx.x	xxx.x	xxx.x
MINIMUM	xxx	xxx	xxx
MAXIMUM	xxx	xxx	xxx
MONTH 3			
N	xxx	xxx	xxx
MEAN	xxx.x	xxx.x	xxx.x
STD	xxx.xx	xxx.xx	xxx.xx
MEDIAN	xxx.x	xxx.x	xxx.x
MINIMUM	xxx	xxx	xxx
MAXIMUM	xxx	xxx	xxx

46

CONFIDENTIAL

RM2009/00475/00  
 VRX-RET-E22-304

Program Path/sas program name

Run Date:

Valeant Pharmaceuticals North America  
Protocol Number: VRX-RET-E22-304

PAGE X OF X

FOOTNOTE: [1] BASELINE PHASE IN STUDY VRX-RET-E22-302

47

CONFIDENTIAL

RM2009/00475/00  
VRX-RET-E22-304

---

Program Path/sas program name

Run Date:

---

Filename: 87272\_304\_SAP\_v2\_final

page 46 of 148

Valeant Pharmaceuticals North America  
Protocol Number: VRX-RET-E22-304

PAGE X OF X

Use Template for TABLE 9.2 to produce:

TABLE 9.3 PERCENTAGE CHANGE IN MONTHLY TOTAL PARTIAL SEIZURE FREQUENCY FOR PATIENTS TREATED WITH RETIGABINE FOR AT LEAST 6 MONTHS DURING THE OPEN-LABEL EXTENSION  
TABLE 9.4 PERCENTAGE CHANGE IN MONTHLY TOTAL PARTIAL SEIZURE FREQUENCY FOR PATIENTS TREATED WITH RETIGABINE FOR AT LEAST 9 MONTHS DURING THE OPEN-LABEL EXTENSION  
TABLE 9.5 PERCENTAGE CHANGE IN MONTHLY TOTAL PARTIAL SEIZURE FREQUENCY FOR PATIENTS TREATED WITH RETIGABINE FOR AT LEAST 12 MONTHS DURING THE OPEN-LABEL EXTENSION  
TABLE 9.6 PERCENTAGE CHANGE IN MONTHLY TOTAL PARTIAL SEIZURE FREQUENCY FOR PATIENTS TREATED WITH RETIGABINE FOR AT LEAST 16 MONTHS DURING THE OPEN-LABEL EXTENSION  
TABLE 9.7 PERCENTAGE CHANGE IN MONTHLY TOTAL PARTIAL SEIZURE FREQUENCY FOR PATIENTS TREATED WITH RETIGABINE FOR AT LEAST 20 MONTHS DURING THE OPEN-LABEL EXTENSION  
TABLE 9.8 PERCENTAGE CHANGE IN MONTHLY TOTAL PARTIAL SEIZURE FREQUENCY FOR PATIENTS TREATED WITH RETIGABINE FOR AT LEAST 24 MONTHS DURING THE OPEN-LABEL EXTENSION  
TABLE 9.9 PERCENTAGE CHANGE IN MONTHLY TOTAL PARTIAL SEIZURE FREQUENCY FOR PATIENTS TREATED WITH RETIGABINE FOR AT LEAST 28 MONTHS DURING THE OPEN-LABEL EXTENSION  
TABLE 9.10 PERCENTAGE CHANGE IN MONTHLY TOTAL PARTIAL SEIZURE FREQUENCY FOR PATIENTS TREATED WITH RETIGABINE FOR AT LEAST 32 MONTHS DURING THE OPEN-LABEL EXTENSION  
TABLE 9.11 PERCENTAGE CHANGE IN MONTHLY TOTAL PARTIAL SEIZURE FREQUENCY FOR PATIENTS TREATED WITH RETIGABINE FOR AT LEAST 36 MONTHS DURING THE OPEN-LABEL EXTENSION

**PROGRAMMING NOTE: EVERY TIMEPOINT SHOULD BE INCLUDED WITHIN THE INDICATED DURATION OF OPEN-LABEL TREATMENT. E.G. MONTHS 1, 3, 6, 9, 12, 16, 20, 24, 28, 32 AND 36 WILL BE PRESENTED IN TABLE 9.11.**

48

CONFIDENTIAL

RM2009/00475/00  
VRX-RET-E22-304

Program Path/sas program name

Run Date:

Valeant Pharmaceuticals North America  
Protocol Number: VRX-RET-E22-304

PAGE X OF X

TABLE 10 RESPONDER RATE ( $\geq 50\%$  REDUCTION IN MONTHLY TOTAL PARTIAL SEIZURE FREQUENCY)  
SAFETY POPULATION

RESPONSE CATEGORY	RETIGABINE (N=XXX)
N	xx
RESPONDERS	xx (xx.x%)
NON-RESPONDERS	xx (xx.x%)

Valeant Pharmaceuticals North America  
Protocol Number: VRX-RET-E22-304

PAGE X OF X

TABLE 11.1 RESPONDER RATE (>=50% REDUCTION IN MONTHLY TOTAL PARTIAL SEIZURE FREQUENCY) FOR PATIENTS TREATED WITH RETIGABINE FOR AT LEAST 1 MONTH DURING THE OPEN-LABEL EXTENSION SAFETY POPULATION

RESPONSE CATEGORY	RETIGABINE (N=XXX)
MONTH 1	
N	xx
RESPONDERS	xx (xx.x%)
NON-RESPONDERS	xx (xx.x%)

50

Program Path/sas program name

Run Date:

Filename: 87272\_304\_SAP\_v2\_final

page 49 of 148

CONFIDENTIAL  
RM2009/00475/00  
VRX-RET-E22-304

Valeant Pharmaceuticals North America  
 Protocol Number: VRX-RET-E22-304

PAGE X OF X

TABLE 11.2 RESPONDER RATE (>=50% REDUCTION IN MONTHLY TOTAL PARTIAL SEIZURE FREQUENCY) FOR PATIENTS TREATED WITH RETIGABINE FOR AT LEAST 3 MONTHS DURING THE OPEN-LABEL EXTENSION SAFETY POPULATION

RESPONSE CATEGORY	RETIGABINE (N=XXX)
MONTH 1	
N	xx
RESPONDERS	xx (xx.x%)
NON-RESPONDERS	xx (xx.x%)
MONTH 3	
N	xx
RESPONDERS	xx (xx.x%)
NON-RESPONDERS	xx (xx.x%)

51

CONFIDENTIAL

RM2009/00475/00  
 VRX-RET-E22-304

Program Path/sas program name

Run Date:

Valeant Pharmaceuticals North America  
Protocol Number: VRX-RET-E22-304

PAGE X OF X

Use Template for TABLE 9.2 to produce:

TABLE 11.3 RESPONDER RATE ( $\geq 50\%$  REDUCTION IN MONTHLY TOTAL PARTIAL SEIZURE FREQUENCY) FOR PATIENTS TREATED WITH RETIGABINE FOR AT LEAST 6 MONTHS DURING THE OPEN-LABEL EXTENSION  
TABLE 11.4 RESPONDER RATE ( $\geq 50\%$  REDUCTION IN MONTHLY TOTAL PARTIAL SEIZURE FREQUENCY) FOR PATIENTS TREATED WITH RETIGABINE FOR AT LEAST 9 MONTHS DURING THE OPEN-LABEL EXTENSION  
TABLE 11.5 RESPONDER RATE ( $\geq 50\%$  REDUCTION IN MONTHLY TOTAL PARTIAL SEIZURE FREQUENCY) FOR PATIENTS TREATED WITH RETIGABINE FOR AT LEAST 12 MONTHS DURING THE OPEN-LABEL EXTENSION  
TABLE 11.6 RESPONDER RATE ( $\geq 50\%$  REDUCTION IN MONTHLY TOTAL PARTIAL SEIZURE FREQUENCY) FOR PATIENTS TREATED WITH RETIGABINE FOR AT LEAST 16 MONTHS DURING THE OPEN-LABEL EXTENSION  
TABLE 11.7 RESPONDER RATE ( $\geq 50\%$  REDUCTION IN MONTHLY TOTAL PARTIAL SEIZURE FREQUENCY) FOR PATIENTS TREATED WITH RETIGABINE FOR AT LEAST 20 MONTHS DURING THE OPEN-LABEL EXTENSION  
TABLE 11.8 RESPONDER RATE ( $\geq 50\%$  REDUCTION IN MONTHLY TOTAL PARTIAL SEIZURE FREQUENCY) FOR PATIENTS TREATED WITH RETIGABINE FOR AT LEAST 24 MONTHS DURING THE OPEN-LABEL EXTENSION  
TABLE 11.9 RESPONDER RATE ( $\geq 50\%$  REDUCTION IN MONTHLY TOTAL PARTIAL SEIZURE FREQUENCY) FOR PATIENTS TREATED WITH RETIGABINE FOR AT LEAST 28 MONTHS DURING THE OPEN-LABEL EXTENSION  
TABLE 11.10 RESPONDER RATE ( $\geq 50\%$  REDUCTION IN MONTHLY TOTAL PARTIAL SEIZURE FREQUENCY) FOR PATIENTS TREATED WITH RETIGABINE FOR AT LEAST 32 MONTHS DURING THE OPEN-LABEL EXTENSION  
TABLE 11.11 RESPONDER RATE ( $\geq 50\%$  REDUCTION IN MONTHLY TOTAL PARTIAL SEIZURE FREQUENCY) FOR PATIENTS TREATED WITH RETIGABINE FOR AT LEAST 36 MONTHS DURING THE OPEN-LABEL EXTENSION

**PROGRAMMING NOTE: EVERY TIMEPOINT SHOULD BE INCLUDED WITHIN THE INDICATED DURATION OF OPEN-LABEL TREATMENT. E.G. MONTHS 1, 3, 6, 9, 12, 16, 20, 24, 28, 32 AND 36 WILL BE PRESENTED IN TABLE 11.11.**

52

CONFIDENTIAL

RM2009/00475/00  
VRX-RET-E22-304

Program Path/sas program name

Run Date:

Valeant Pharmaceuticals North America  
Protocol Number: VRX-RET-E22-304

PAGE X OF X

TABLE 12 PROPORTION OF PATIENTS EXPERIENCING A REDUCTION IN MONTHLY TOTAL PARTIAL SEIZURE FREQUENCY  
SAFETY POPULATION

CATEGORY	RETIGABINE (N=XXX)
REDUCTION CATEGORY	
[-100%, -75%]	xx (xx.x%)
(- 75%, -50%]	xx (xx.x%)
(- 50%, -25%]	xx (xx.x%)
(- 25%, 0%)	xx (xx.x%)
WITHOUT REDUCTION	xx (xx.x%)

53

CONFIDENTIAL

RM2009/00475/00  
VRX-RET-E22-304

Program Path/sas program name

Run Date:

TABLE 13 PROPORTION OF SEIZURE-FREE DAYS  
SAFETY POPULATION

STATISTICS	RETIGABINE (N=XXX)
SEIZURE-FREE DAYS (%)	
N	xxx
MEAN	xxx.x
STD	xxx.xx
MEDIAN	xxx.x
MINIMUM	xxx
MAXIMUM	xxx
REDUCTION CATEGORY	
SEIZURE-FREE [=100%]	xx (xx.x%)
NOT SEIZURE-FREE	xx (xx.x%)
[95%, 100%]	xx (xx.x%)
[75%, 95%]	xx (xx.x%)
[50%, 75%]	xx (xx.x%)
[50%, 25%]	xx (xx.x%)
[0%, 25%]	xx (xx.x%)
NUMBER OF PATIENTS WHO WERE SEIZURE-FREE FOR	
6 MONTHS	xx (xx.x%)
12 MONTHS	xx (xx.x%)

54

CONFIDENTIAL

RM2009/00475/00  
VRX-RET-E22-304

TABLE 14 EXTENT OF EXPOSURE TO STUDY MEDICATION  
 SAFETY POPULATION

STATISTICS	RETIGABINE (N=XXX)
EXTENT OF EXPOSURE (DAYS)	
N	xxx
MEAN	xxx.x
STD	xxx.xx
MEDIAN	xxx.x
MINIMUM	xxx
MAXIMUM	xxx
RETIGABINE EXPOSURE CATEGORY (MONTHS)	
N	xxx (100.0%)
[0, 1]	xxx ( xx.x%)
(1, 3]	xxx ( xx.x%)
(3, 6]	xxx ( xx.x%)
(6, 9]	xxx ( xx.x%)
(9, 12]	xxx ( xx.x%)
(12,16]	xxx ( xx.x%)
(16,20]	xxx ( xx.x%)
(20,24]	xxx ( xx.x%)
(24,28]	xxx ( xx.x%)
(28,32]	xxx ( xx.x%)
(32,36]	xxx ( xx.x%)
>36	
DAILY DOSE OF RETIGABINE EXPOSURE (MG)	
N	xxx
MEAN	xxx.x
STD	xxx.xx
MEDIAN	xxx.x
MINIMUM	xxx
MAXIMUM	xxx

55

CONFIDENTIAL

RM2009/00475/00  
 VRX-RET-E22-304

TABLE 15 NUMBER (%) OF PATIENTS REPORTING TREATMENT-EMERGENT ADVERSE EVENTS  
 SAFETY POPULATION

SYSTEM ORGAN CLASS PREFERRED TERM	RETIGABINE (N=XXX)
ANY ADVERSE EVENT	xxx ( xx.x%)
1ST SYSTEM ORGAN CLASS PREFERRED TERMS BELOW	xxx ( xx.x%) xxx ( xx.x%)
2ND SYSTEM ORGAN CLASS PREFERRED TERMS BELOW	xxx ( xx.x%) xxx ( xx.x%)

Valeant Pharmaceuticals North America  
 Protocol Number: VRX-RET-E22-304

PAGE X OF X

TABLE 16 NUMBER (%) OF PATIENTS REPORTING ADVERSE EVENTS BY MAXIMUM SEVERITY  
 SAFETY POPULATION

SYSTEM ORGAN CLASS PREFERRED TERM	RETIGABINE (N=XXX)		
	MILD	MODERATE	SEVERE
1ST SYSTEM ORGAN CLASS PREFERRED TERMS BELOW	xxx ( xx.x%)	xxx ( xx.x%)	xxx ( xx.x%)
2ND SYSTEM ORGAN CLASS PREFERRED TERMS BELOW	xxx ( xx.x%)	xxx ( xx.x%)	xxx ( xx.x%)

57

CONFIDENTIAL

RM2009/00475/00  
 VRX-RET-E22-304

Program Path/sas program name

Run Date:

Valeant Pharmaceuticals North America  
Protocol Number: VRX-RET-E22-304

PAGE X OF X

Use Template for TABLE 15 to produce:

TABLE 17 NUMBER (%) OF PATIENTS REPORTING TREATMENT-EMERGENT ADVERSE EVENTS AT LEAST POSSIBLY RELATED TO STUDY DRUG  
TABLE 18 NUMBER (%) OF PATIENTS REPORTING TREATMENT-EMERGENT ADVERSE EVENTS THAT LEAD TO DOSE MODIFICATION/INTERRUPTION  
TABLE 19 NUMBER (%) OF PATIENTS REPORTING FATAL TREATMENT-EMERGENT ADVERSE EVENTS  
TABLE 20 NUMBER (%) OF PATIENTS REPORTING SERIOUS TREATMENT-EMERGENT ADVERSE EVENTS  
TABLE 21 NUMBER (%) OF PATIENTS REPORTING ADVERSE EVENTS THAT CAUSED WITHDRAWAL FROM STUDY

Valeant Pharmaceuticals North America  
 Protocol Number: VRX-RET-E22-304

PAGE X OF X

TABLE 22 OBSERVED MEANS AND STANDARD DEVIATIONS OF LABORATORY TEST RESULTS AND CHANGE FROM BASELINE BY MONTH - SERUM CHEMISTRY SAFETY POPULATION

TEST NAME (TEST UNIT)	TIMEPOINT	n	RETIGABINE (N=XXX)		Change from Baseline Mean (STD)
			Mean	(STD)	
SODIUM (MMOL/L)	BASELINE	xxx	xx.x	(xx.xx)	
	MONTH 1	xxx	xx.x	(xx.xx)	xx.x (xx.xx)
	MONTH 3	xxx	xx.x	(xx.xx)	xx.x (xx.xx)
	MONTH 6	xxx	xx.x	(xx.xx)	xx.x (xx.xx)
	MONTH 9	xxx	xx.x	(xx.xx)	xx.x (xx.xx)
	MONTH 12	xxx	xx.x	(xx.xx)	xx.x (xx.xx)
	MONTH 16	xxx	xx.x	(xx.xx)	xx.x (xx.xx)
	MONTH 20	xxx	xx.x	(xx.xx)	xx.x (xx.xx)
	MONTH 24	xxx	xx.x	(xx.xx)	xx.x (xx.xx)
	MONTH 28	xxx	xx.x	(xx.xx)	xx.x (xx.xx)
	MONTH 32	xxx	xx.x	(xx.xx)	xx.x (xx.xx)
	MONTH 36	xxx	xx.x	(xx.xx)	xx.x (xx.xx)
POTASSIUM (MMOL/L)	:				

59

CONFIDENTIAL

Use Template for TABLE 22 to produce:

TABLE 24 OBSERVED MEANS AND STANDARD DEVIATIONS OF LABORATORY TEST RESULTS AND CHANGE FROM BASELINE BY MONTH - HEMATOLOGY  
 TABLE 25 OBSERVED MEANS AND STANDARD DEVIATIONS OF LABORATORY TEST RESULTS AND CHANGE FROM BASELINE BY MONTH - URINALYSIS

Program Path/sas program name

Run Date:

RM2009/00475/00  
 VRX-RET-E22-304

Valeant Pharmaceuticals North America  
 Protocol Number: VRX-RET-E22-304

PAGE X OF X

TABLE 23 NUMBER (%) OF PATIENTS WITH CLINICALLY SIGNIFICANT LIVER FUNCTION TEST RESULTS  
 SAFETY POPULATION

TEST NAME (TEST UNIT)	TIMEPOINT	RETIGABINE (N=XXX)			
		n	>3xULN	>5xULN	>10xULN
ALT (MMOL/L)	BASELINE	xxx	xx.x (xx.xx)	xx.x (xx.xx)	xx.x (xx.xx)
	MONTH 1	xxx	xx.x (xx.xx)	xx.x (xx.xx)	xx.x (xx.xx)
	MONTH 3	xxx	xx.x (xx.xx)	xx.x (xx.xx)	xx.x (xx.xx)
	MONTH 6	xxx	xx.x (xx.xx)	xx.x (xx.xx)	xx.x (xx.xx)
	MONTH 9	xxx	xx.x (xx.xx)	xx.x (xx.xx)	xx.x (xx.xx)
	MONTH 12	xxx	xx.x (xx.xx)	xx.x (xx.xx)	xx.x (xx.xx)
	MONTH 16	xxx	xx.x (xx.xx)	xx.x (xx.xx)	xx.x (xx.xx)
	MONTH 20	xxx	xx.x (xx.xx)	xx.x (xx.xx)	xx.x (xx.xx)
	MONTH 24	xxx	xx.x (xx.xx)	xx.x (xx.xx)	xx.x (xx.xx)
	MONTH 28	xxx	xx.x (xx.xx)	xx.x (xx.xx)	xx.x (xx.xx)
	MONTH 32	xxx	xx.x (xx.xx)	xx.x (xx.xx)	xx.x (xx.xx)
	MONTH 36	xxx	xx.x (xx.xx)	xx.x (xx.xx)	xx.x (xx.xx)
	AST (MMOL/L)				

REPEAT FOR TOTAL BILIRUBIN AND ALKALINE PHOSPHATASE

Program Path/sas program name

Run Date:

Valeant Pharmaceuticals North America  
 Protocol Number: VRX-RET-E22-304

PAGE X OF X

TABLE 26 FREQUENCY DISTRIBUTION OF CATEGORICAL LABORATORY TEST RESULTS - URINALYSIS  
 SAFETY POPULATION

	RETIGABINE (N=XXX)
TEST NAME	
MONTH 1	
1+	xx (xx.x%)
2+	xx (xx.x%)
3+	xx (xx.x%)
4+	xx (xx.x%)
MONTH 3	
1+	xx (xx.x%)
2+	xx (xx.x%)
3+	xx (xx.x%)
4+	xx (xx.x%)
MONTH 6	
MONTH 9	
MONTH 12	
MONTH 16	
MONTH 20	
MONTH 24	
MONTH 28	
MONTH 32	
MONTH 36	

REPEAT FOR ALL NON-NUMERIC TEST RESULTS

Program Path/sas program name

Run Date:

TABLE 27 SUMMARY STATISTICS OF ELECTROCARDIOGRAM MEASURES  
 SAFETY POPULATION

TIMEPOINT	EVALUATION - UNIT STATISTIC	RETIGABINE (N=XXX)
BASELINE AVG	VENTRICULAR RATE - BPM	
	N	xxx
	MEAN	xxx.x
	STD	xxx.xx
	MEDIAN	xxx.x
	MINIMUM	xxx
	MAXIMUM	xxx
	RR INTERVAL - MS	
	N	xxx
	MEAN	xxx.x
	STD	xxx.xx
	MEDIAN	xxx.x
	MINIMUM	xxx
	MAXIMUM	xxx
	PR INTERVAL - MS	
	N	xxx
	MEAN	xxx.x
	STD	xxx.xx
	MEDIAN	xxx.x
	MINIMUM	xxx
	MAXIMUM	xxx
QRS INTERVAL - MS		
N	xxx	
MEAN	xxx.x	
STD	xxx.xx	
MEDIAN	xxx.x	
MINIMUM	xxx	
MAXIMUM	xxx	

62

CONFIDENTIAL

RM2009/00475/00  
 VRX-RET-E22-304

Valeant Pharmaceuticals North America  
 Protocol Number: VRX-RET-E22-304

PAGE X OF X

TABLE 27 SUMMARY STATISTICS OF ELECTROCARDIOGRAM MEASURES  
 SAFETY POPULATION

TIMEPOINT	EVALUATION - UNIT STATISTIC	RETIGABINE (N=XXX)
BASELINE AVG (CONTINUED)	QT INTERVAL - MS	
	N	xxx
	MEAN	xxx.x
	STD	xxx.xx
	MEDIAN	xxx.x
	MINIMUM	xxx
	MAXIMUM	xxx
	QTc INTERVAL BAZETT - MS	
	N	xxx
	MEAN	xxx.x
	STD	xxx.xx
	MEDIAN	xxx.x
	MINIMUM	xxx
	MAXIMUM	xxx
	QTc INTERVAL FRIDERICIA - MS	
	N	xxx
	MEAN	xxx.x
	STD	xxx.xx
MEDIAN	xxx.x	
MINIMUM	xxx	
MAXIMUM	xxx	

REPEAT FOR TIMEPOINTS MONTH 1, MONTH 3, MONTH 6, MONTH 9, MONTH 12, MONTH 24, MONTH 36

Program Path/sas program name

Run Date:

Filename: 87272\_304\_SAP\_v2\_final

page 62 of 148

Valeant Pharmaceuticals North America  
 Protocol Number: VRX-RET-E22-304

PAGE X OF X

TABLE 28 NUMBER (%) OF PATIENTS EXAMINING QTc INTERVAL BY CATEGORY  
 SAFETY POPULATION

TIMEPOINT	CATEGORY	RETIGABINE (N=XXX)
BASELINE AVG (CONTINUED)	ABSOLUTE QTc INTERVAL (MS)	
	FRIDERICIA'S CORRECTION	
	<= 450	xx (xx.x%)
	(450, 480]	xx (xx.x%)
	(480, 500]	xx (xx.x%)
	> 500	xx (xx.x%)
	BAZETT'S CORRECTION	
	<= 450	xx (xx.x%)
	(450, 480]	xx (xx.x%)
	(480, 500]	xx (xx.x%)
> 500	xx (xx.x%)	

REPEAT FOR TIMEPOINTS MONTH 1, MONTH 3, MONTH 6, MONTH 9, MONTH 12, MONTH 24, MONTH 36

64

Program Path/sas program name

Run Date:

Filename: 87272\_304\_SAP\_v2\_final

page 63 of 148

CONFIDENTIAL  
 RM2009/00475/00  
 VRX-RET-E22-304

TABLE 29 NUMBER (%) OF PATIENTS EXAMINING QTC INTERVAL CHANGE FROM BASELINE BY CATEGORY  
 SAFETY POPULATION

TIMEPOINT	CATEGORY	RETIGABINE (N=XXX)
MONTH 1	CHANGE FROM BASELINE IN QTC INTERVAL (MS)	
	FRIDERICIA'S CORRECTION	
	<= 30	xx (xx.x%)
	(30, 60]	xx (xx.x%)
	> 60	xx (xx.x%)
	BAZETT'S CORRECTION	
	<= 30	xx (xx.x%)
	(30, 60]	xx (xx.x%)
	> 60	xx (xx.x%)

REPEAT FOR TIMEPOINTS MONTH 3, MONTH 6, MONTH 9, MONTH 12, MONTH 24, MONTH 36

65

TABLE 30 OBSERVED MEANS AND STANDARD DEVIATIONS OF QTc INTERVALS AND CHANGE FROM BASELINE BY MONTH SAFETY POPULATION

TIMEPOINT	n	RETIGABINE (N=XXX)	
		Mean (STD)	Change from Baseline Mean (STD)
ABSOLUTE QTc (FRIDERICIA'S) INTERVAL (MS)			
MONTH 1	xxx	xx.x (xx.xx)	xx.x (xx.xx)
MONTH 3	xxx	xx.x (xx.xx)	xx.x (xx.xx)
MONTH 6	xxx	xx.x (xx.xx)	xx.x (xx.xx)
MONTH 9	xxx	xx.x (xx.xx)	xx.x (xx.xx)
MONTH 12	xxx	xx.x (xx.xx)	xx.x (xx.xx)
MONTH 24	xxx	xx.x (xx.xx)	xx.x (xx.xx)
MONTH 36	xxx	xx.x (xx.xx)	xx.x (xx.xx)
ABSOLUTE QTc (BAZETT'S) INTERVAL (MS)			
MONTH 1	xxx	xx.x (xx.xx)	xx.x (xx.xx)
MONTH 3	xxx	xx.x (xx.xx)	xx.x (xx.xx)
MONTH 6	xxx	xx.x (xx.xx)	xx.x (xx.xx)
MONTH 9	xxx	xx.x (xx.xx)	xx.x (xx.xx)
MONTH 12	xxx	xx.x (xx.xx)	xx.x (xx.xx)
MONTH 24	xxx	xx.x (xx.xx)	xx.x (xx.xx)
MONTH 36	xxx	xx.x (xx.xx)	xx.x (xx.xx)

66

CONFIDENTIAL

RM2009/00475/00  
 VRX-RET-E22-304

TABLE 31 OBSERVED MEANS AND STANDARD DEVIATIONS OF VITAL SIGN RESULTS AND CHANGE FROM BASELINE BY MONTH  
 SAFETY POPULATION

PARAMETER (PARAMETER UNIT)	TIMEPOINT	n	RETIGABINE (N=XXX)	
			Mean (STD)	Change from Baseline Mean (STD)
SUPINE SBP (MMHG)	BASELINE	xxx	xx.x (xx.xx)	
	MONTH 1	xxx	xx.x (xx.xx)	xx.x (xx.xx)
	MONTH 3	xxx	xx.x (xx.xx)	xx.x (xx.xx)
	MONTH 6	xxx	xx.x (xx.xx)	xx.x (xx.xx)
	MONTH 9	xxx	xx.x (xx.xx)	xx.x (xx.xx)
	MONTH 12	xxx	xx.x (xx.xx)	xx.x (xx.xx)
	MONTH 16	xxx	xx.x (xx.xx)	xx.x (xx.xx)
	MONTH 20	xxx	xx.x (xx.xx)	xx.x (xx.xx)
	MONTH 24	xxx	xx.x (xx.xx)	xx.x (xx.xx)
	MONTH 28	xxx	xx.x (xx.xx)	xx.x (xx.xx)
	MONTH 32	xxx	xx.x (xx.xx)	xx.x (xx.xx)
	MONTH 36	xxx	xx.x (xx.xx)	xx.x (xx.xx)
	SUPINE DBP (MMHG)	:		

67

CONFIDENTIAL

RM2009/00475/00  
 VRX-RET-E22-304

TABLE 32 NUMBER (%) OF PATIENTS WITH ORTHOSTATIC HYPOTENSION  
 SAFETY POPULATION

TIMEPOINT		RETIGABINE (N=XXX)
BASELINE	N	xx
	YES	xx (xx.x%)
	NO	xx (xx.x%)
MONTH 1	N	xx
	YES	xx (xx.x%)
	NO	xx (xx.x%)
MONTH 3	N	xx
	YES	xx (xx.x%)
	NO	xx (xx.x%)
MONTH 6	N	xx
	YES	xx (xx.x%)
	NO	xx (xx.x%)
MONTH 9	N	xx
	YES	xx (xx.x%)
	NO	xx (xx.x%)
MONTH 12	N	xx
	YES	xx (xx.x%)
	NO	xx (xx.x%)

REPEAT FOR TIMEPOINTS MONTH 16, MONTH 20, MONTH 24, MONTH 28, MONTH 32 AND MONTH 36

FOOTNOTES:  
 ORTHOSTATIC HYPOTENSION IS DEFINED AS EITHER A DECREASE IN SBP>=20 MMHG UPON STANDING OR DECREASE IN DBP>=10 MMHG UPON STANDING

Program Path/sas program name

Run Date:

Valeant Pharmaceuticals North America  
Protocol Number: VRX-RET-E22-304

PAGE X OF X

69

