### 7.3. Preclinical Safety Studies

Retigabine caused motor impairment in rodents in the rotarod test, but the doses necessary were 12 to 13 times higher than those active in models of epilepsy. Neither retigabine nor its N-acetyl metabolite prolonged action potential duration (APD) in cat cardiac myocytes and dog Purkinje fibers, and in fact resulted in slight shortening of APD in these test systems. At concentrations 17-20 times higher than those achieved at therapeutic doses in man, retigabine caused a slight prolongation in QT interval in the isolated guinea pig heart, as well as a slight reduction in K+ current through human ether-a-go-go related gene (hERG) channels. However, retigabine did not affect ECG parameters in anesthetized dogs or conscious unrestrained dogs given daily doses for 7 days. Retigabine may inhibit bladder contractions and micturition in rodents due to its ability to hyperpolarize and stabilize urinary bladder myocytes through activation of K+ channels.

In acute and chronic toxicity studies in rats, CNS related clinical signs including hyperkinesia, hypokinesia, disturbed coordination, stilted gait, tremor and convulsions were observed. In repeat dose toxicity studies in rodents, slight hepatocellular and thyroid follicular hypertrophy were observed and were considered to be adaptive. In repeat-dose studies in dogs but not rodents, self-limiting hepatocellular degeneration was observed in regions adjacent to the gallbladder. In rodents but not dogs, distended urinary bladder or urinary bladder ectasia was noted with occasional secondary inflammation and ulceration of bladder wall.

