**10.20.1. Reasons for Withdrawal**

Patients are free to discontinue their participation in the study at any time and without prejudice to further treatment at their local site. The Investigator must withdraw any patient from the study if that patient requests to be withdrawn.

Patients withdrawn from the study will not be replaced, regardless of the reason for withdrawal. The patient's participation in this study may be discontinued due to the following reasons:

- Patient experiences an intolerable AE.
- Investigator decides patient has an "unsatisfactory response – efficacy."
- Patient becomes pregnant.
- Patient is unwilling or unable to continue the study.
- Patient is non-compliant with study procedures.
- Patient needs medication not allowed in the protocol.
- Any clinically significant change in patient's medical condition.
- Persistent ALT or aspartate aminotransferase (AST) above 3 times the ULN; will be confirmed by repeating laboratory assessment within 1 week.
- ALT or AST levels are above 5 times the ULN at any time during the study.
- Confirmed QTc prolongation defined as QTc (Bazett's) >500 msec or an increase in QTc (Bazett's) of >60 msec from baseline.
- Investigator decides that withdrawal from the study is in the best interest of the patient.
- Request of the Sponsor
- Hematological reasons or infections – for all such patients, the investigator shall report these in an expedited manner, whether or not they are considered serious or unexpected.

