## 4 STATISTICAL METHODS

### 4.1 Study Patients

#### 4.1.1 Disposition of Patients

Patients are free to discontinue their participation in the study at any time and without prejudice to further treatment at their local site. The Investigator must withdraw any patient from the study if that patient requests to be withdrawn. Patients withdrawn from the study will not be replaced, regardless of the reason for withdrawal. The patient's participation in this study may be discontinued due to the following reasons:

- Patient experiences an intolerable AE.
- Investigator decides patient has an “unsatisfactory response – efficacy.”
- Patient becomes pregnant.
- Patient is unwilling or unable to continue the study.
- Patient is non-compliant with study procedures.
- Patient needs medication not allowed in the protocol.
- Any clinically significant change in patient's medical condition.
- Persistent ALT or aspartate aminotransferase (AST) above 3 times the ULN; will be confirmed by repeating laboratory assessment within 1 week.
- ALT or AST levels are above 5 times the ULN at any time during the study.
- Confirmed QTc prolongation defined as QTc (Bazett's) >500 msec or an increase in QTc (Bazett's) of >60 msec from baseline.

- Investigator decides that withdrawal from the study is in the best interest of the patient.
- Request of the Sponsor.
- Hematological reasons or infections – for all such patients, the investigator shall report these in an expedited manner, whether or not they are considered serious or unexpected.

A summary of the number and percentage of discontinuations by primary reason will be provided together with descriptive statistics for the time until treatment discontinuation (days).

A by-patient listing of patient withdrawal/study completion details will also be provided.

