#### 4.5.4 Clinical Laboratory Evaluation

All clinical laboratory assessments are implemented by a central laboratory.

The clinical laboratory data were collected at baseline, Months 1, 3, 6, 9, 12, 16, 20, 24, 28, 32, and 36. Additional hematological assessments are collected at Months 2, 4, 8 and 10.

The laboratory data include:

1. Hematology: hemoglobin, hematocrit, RBC count, WBC count with differential, and platelet count.
2. Blood chemistries: sodium, potassium, chloride, bicarbonate, glucose, cholesterol, creatinine, calcium, phosphorus, BUN, uric acid, total bilirubin, total protein, AST, ALT, and alkaline phosphatase levels.
3. Routine urinalysis: specific gravity, pH, protein/albumin, glucose/sugar, ketones/acetone, and hemoglobin/blood. In order to standardize measurements, Bayer multistix 8-SG or equivalent dipsticks will be used.
4. Microscopic urinalysis: RBC, WBC, casts, and crystals/cells.

Descriptive statistics for laboratory results and change from baseline for each visit will be presented separately for hematology, biochemistry and urinalysis parameters. The number of patients with clinically significant liver function tests will also be presented.

A by-patient listing of all laboratory data will also be provided with abnormal values highlighted, and including centre, patient identifier, age, sex, race, weight and visit. A listing of the central laboratory reference ranges will also be provided.

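### Table 23 counts bilirubin and alkaline phosphatase rises only above the ALT/AST cut-offs, and no table counts patients with ALT/AST and bilirubin raised together

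*SAP*

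**What the plan says.** The shell in SAP Section 10 is titled "TABLE 23 NUMBER (%) OF PATIENTS WITH CLINICALLY SIGNIFICANT LIVER FUNCTION TEST RESULTS". It has three columns (>3x, >5x and >10x ULN) and rows by visit from baseline to Month 36 for ALT and AST. A note below it reads "REPEAT FOR TOTAL BILIRUBIN AND ALKALINE PHOSPHATASE". No separate cut-offs follow for those two tests.

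The text behind the table, SAP 4.5.4, says only: "The number of patients with clinically significant liver function tests will also be presented". It does not define clinically significant, so the columns of Table 23 become the definition.

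Elsewhere, multiples of the ULN appear only for ALT and AST, as reasons for withdrawal. SAP 4.1.1 has "Persistent ALT or aspartate aminotransferase (AST) above 3 times the ULN", and Protocol 10.20.1 has "ALT or AST levels are above 5 times the ULN at any time during the study". Neither document gives a limit for bilirubin or ALP.

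Those two tests are otherwise shown in two places. One is "TABLE 22 OBSERVED MEANS AND STANDARD DEVIATIONS OF LABORATORY TEST RESULTS AND CHANGE FROM BASELINE BY MONTH - SERUM CHEMISTRY", which gives means, standard deviations and changes. The other is Listing 20, under the SAP 4.5.4 commitment: "A by-patient listing of all laboratory data will also be provided with abnormal values highlighted".

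**The concern.** The columns match the ALT/AST withdrawal limits and were carried over to two other tests with no reason given. Elsewhere the SAP sets limits for each measure separately: QTc bands, blood pressure drops for orthostatic hypotension, AUA score bands and PVR volumes. The liver table is the exception.

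Two things follow. Under a title about clinically significant results, a bilirubin of 2.9x ULN counts as zero. And because each test is tabulated alone, the table cannot show how many patients had an aminotransferase rise and a bilirubin rise together.

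This matters because safety is the primary objective, exposure runs for years and there is no comparator arm. Counts of outlying values are then the main way a table can show uncommon liver abnormalities.

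**Working it through.** The plan states no figure on this point, so there is nothing to reproduce. The check applies the shell's rules to example patients.

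**Inputs.** The cut-offs of 3, 5 and 10 times ULN come from Table 23. N = 510 is the approximate maximum in SAP 4.7. The patient values, the marginal counts and the bilirubin ULN (1.0 to 1.2 mg/dL) are assumptions, because the documents give no liver-test rates or reference ranges.

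**Step 1: which columns each patient enters.** A result is counted if it is strictly above the cut-off.

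| Patient | ALT (x ULN) | Bilirubin (x ULN) | ALT columns | Bilirubin columns |
|---|---|---|---|---|
| A | 4 | 2.5 | >3x | none |
| B | 4 | 3.5 | >3x | >3x |
| C | 2 | 2.9 | none | none |
| D | 4 | 0.8 | >3x | none |
| E | 0.9 | 3.5 | none | >3x |

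A adds to the ALT count only. C is counted nowhere.

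**Step 2: the same limits in mg/dL.** At a ULN of 1.2, the first bilirubin column starts above 3 x 1.2 = 3.6 and the last above 10 x 1.2 = 12. Patient A has 2.5 x 1.2 = 3.0. At a ULN of 1.0, the limits are 3.0 and 10, and patient A has 2.5.

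**Step 3: can combined cases be recovered from separate counts?** B plus one patient with normal results gives the same entries as D plus E, so no. In general, if a patients exceed the ALT limit and b exceed the bilirubin limit, the number exceeding both lies between max(0, a + b - N) and min(a, b). With a = 10 and b = 3, the lower bound is max(0, 13 - 510) = 0 and the upper bound is 3. With a = 10 and b = 5, the range is 0 to 5. The separate counts rule out nothing below the smaller one.

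**Step 4: would Table 22 show it?** One patient rising from an assumed 0.6 to 3.0 mg/dL moves the mean by 2.4/510 = 0.005 mg/dL, or by 2.4/200 = 0.012 with 200 patients at the visit. A mean cannot show a single case.

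**The case against.** A reader might infer that these cases are invisible. They are not. Listing 20 puts ALT, AST, ALP and total bilirubin in adjacent columns, by patient and visit, with an H flag on high values. Patient A would be there with both results flagged. Persistent ALT/AST above 3x ULN is a withdrawal reason with its own row in Table 1. Under Protocol 10.3.4, a laboratory abnormality that leads to intervention, a dose change or other treatment, or goes with another diagnosis, can be reported as an adverse event. This part of the objection stands.

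These routes are partial, however. Table 1 has no bilirubin or ALP row. A rise that meets none of the adverse event conditions need not be reported as one. The H flag does not grade the rise, and the SAP does not ask anyone to search the listing for combined cases.

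A reader might also infer that the animal work amounts to a liver signal. Protocol 7.3 does not support that: in dogs, "self-limiting hepatocellular degeneration was observed in regions adjacent to the gallbladder", and the rodent liver changes were considered adaptive. Protocol 7.4 reports few clinically important laboratory changes in the 397-patient controlled study. The Hungarian addendum adds GGT testing at local laboratories and says nothing about bilirubin limits.

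Finally, neither document supplies a bilirubin or ALP limit, so any replacement is a reporting convention for the sponsor to confirm. That also stands, but it limits the choice of numbers. It does not justify borrowing the ALT/AST columns without comment.

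**Conclusion.** The point holds for counting. As the shell is written, bilirubin and ALP rises up to and including 3x ULN enter no count in the only table of clinically significant liver tests, and no table counts ALT/AST and bilirubin raised in the same patient. This rests on the shell alone and not on any assumed ULN or event rate.

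How many patients are affected cannot be estimated, because the documents give no liver-test rates. The documents also do not support saying that the trial would conclude there was no important bilirubin change: no planned test or conclusion depends on Table 23 alone, and the individual values are listed. This is an insensitive summary in a safety study. It should be corrected, but it does not threaten the data or the conduct of the trial.

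**What to change.** In Table 23:

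- Keep >3x, >5x and >10x ULN for ALT and AST.
- Give total bilirubin and ALP their own lower columns, for example >1.5x, >2x and >3x ULN. These values are an assumption for the sponsor to confirm.
- Add one row: number (%) of patients with ALT or AST >3x ULN and raised bilirubin (for example >2x ULN, also to be confirmed) in the same on-treatment sample. Support it with a short listing of those patients that includes ALP.
- Correct the cells, which are laid out as mean (SD) under a number (%) title, and the ALT/AST units, which are mmol/L here and IU/L in Listing 20.

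Matching within one sample is enough. Scheduled post-baseline chemistry visits are closest at Months 1 and 3. With 30-day months and windows of 3 and 7 days, they are at least 60 - 3 - 7 = 50 days apart. A short matching window across samples would therefore add only repeat or unscheduled tests.

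All four tests are already in the chemistry panel. The cost is a revised shell, a little programming and one short listing, and a few more patients will be shown as abnormal. These are reporting limits only and change no withdrawal rule.
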